Each year in the US approximately 100,000 people begin chronic dialysis and 80,000 die resulting in the growth of the prevalent population which now exceeds 400,000 patients on chronic dialysis. Prevalent HD patients have a mortality rate of 20% per year. Even more disconcerting is that during the first six months of therapy the annualized mortality is 35-40%. Although many clinical trials have examined the extent to which outcomes could be improved in the prevalent dialysis population, incident HD patients have been largely overlooked despite their high mortality, morbidity and marked decrements in HRQOL. This proposal addresses the crisis of care in incident HD patients by focusing on maintaining RRF, one of the strongest predictors of survival and HRQOL in the first year of dialysis therapy.

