### **3. Study Design**

This pilot RCT will demonstrate the feasibility and safety of performing a large scale study of diuretic use and/or cool dialysate by examining recruitment, retention, and key outcomes. This study will further assess whether the use of a diuretic compared to non-use of a diuretic (placebo) and/or the use of cool dialysate (35.5 °C) compared to 37 °C for up to 6 months will improve RRF, improve HRQOL and reduce hospitalizations. by randomizing 20 chronic hemodialysis patients from DCI centers in the greater Albuquerque area, to either bumetanide and cool dialysate randomized in a two-by-two factorial distribution.

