# DIDIT: Diuretic/Cool Dialysate Trial

No Diuretic (placebo) and 37°C dialysate	No Diuretic (placebo) and 35.5°C dialysate
Diuretic and 37°C dialysate	Diuretic and 35.5°C dialysate

The study sample will be selected using an approach to limit drop-out while enhancing generalizability and the main analysis will be intention-to-treat. *Considering the intervention cannot be double-blinded, we have made efforts to reduce bias by using objective outcomes and blinding the assessment of patient-reported outcomes.* Subjects will be recruited for 18 months. An additional 6 month period will be used to complete the intervention in the last subjects and they will be re-assessed at month 8 for an end of study evaluation. The recruitment and participation parameters for development of this formal RCT will assess whether the large scale study can meet enrollment criteria and target timelines, and whether patients can be maintained on the study protocol without safety concerns.

In this pilot study we will assess as primary patient outcomes:

- The change in RRF over 6 months
- The association of cool dialysis and/or diuretic with inflammation
- The association of cool dialysis and/or diuretic use with acute kidney injury (AKI) biomarkers.

The secondary patient outcomes will be:

- Change in HRQOL
- Time to first-hospitalization.

Being a pilot study, our focus is on assessing whether changes in RRF can be detected with the proposed technique (urinary creatinine and urea clearance). Biomarkers of inflammation and AKI will be collected to supplement the functional measurement of renal filtration and as surrogate biomarkers of benefit or safety (e.g. nephrotoxicity) that can be monitored in the large scale study.

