## 13. Data Analysis

For both studies, patient characteristics and outcomes will be summarized by study arm. Primary outcomes include 6-month change in RRF. Differences between baseline and 6 months will be calculated and analyzed with a mixed model that incorporates potentially important covariates, such as age, gender and ethnicity. For measurements that will be taken monthly, such as albumin, a repeated measures analysis of variance also will be conducted on the measurements rather than the differences. If needed, transformations or analyses based on ranks will be utilized. This approach will also be used for other outcomes that can be treated as continuous variables, such as HRQOL, inflammatory markers and the number of days of hospitalization. For discrete variables, such as the number of hospitalizations, either logistic regression or Poisson regression will be used. The time to first hospitalization will be examined using Kaplan-Meier plots. To adjust for study site and baseline covariates, the proportional hazards model will be used. All analyses will be intent-to-treat, in that patients will be included in analyses regardless of whether the intervention was applied as intended. Estimates of mean change will be obtained along with 95% confidence intervals. All analyses will be conducted in SAS.

This pilot study will inform the design of a larger clinical trial. For Specific Aim 2, the proportions recruited and retained will be estimated. With a recruitment and randomization of 20 patients, the proportion retained can be estimated to within  $\pm 0.18$  with a 95% confidence interval. Estimates of mean changes, along with estimates of variability, will be obtained and used in designing the larger clinical trial.

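### Hospital days, admission counts and time to first hospitalization are analysed with no allowance for death, so an arm with more deaths can look modestly better on days and counts

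*Combined protocol and SAP*

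**What the plan says.** Section 3 (Study Design) asks whether the interventions, given for up to six months, "will improve RRF, improve HRQOL and reduce hospitalizations". Its only listed hospitalization outcome is a secondary one: "Time to first-hospitalization".

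Section 13 (Data Analysis) sets out three hospitalization analyses:

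- Days in hospital are grouped with outcomes that can be treated as continuous: "HRQOL, inflammatory markers and the number of days of hospitalization".
- Counts: "For discrete variables, such as the number of hospitalizations, either logistic regression or Poisson regression will be used".
- Time to event: "The time to first hospitalization will be examined using Kaplan-Meier plots". Then: "To adjust for study site and baseline covariates, the proportional hazards model will be used".

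On mortality, Section 2 (Background) says that "during the first six months of therapy the annualized mortality is 35-40" per cent, and also that "Prevalent HD patients have a mortality rate of 20% per year". Section 1 includes lower mortality in the hypothesis, and Table 1 in Section 12 records mortality among the adverse events. Death is not among the primary or secondary outcomes in Section 3.

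No section says how a death enters any of the three analyses. There is no composite with death, competing-risk method, censoring rule, term for time alive, or rule for hospital days after death. The intention-to-treat sentence in Section 13 concerns only whether the intervention was delivered as planned.

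**The concern.** A patient who dies early has less time in which to be admitted. An analysis of raw hospital days or raw admission counts reads that lost time as less hospital use. If one arm has more deaths, by effect or by chance, part of the excess mortality appears as a reduction in hospitalization. For time to first hospitalization, a death before any admission is not an event, so excess deaths leave no direct trace in the result.

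Section 13 says that the pilot's mean changes and variability will be used to design the larger trial, and Section 7 lists health care utilization among the data collected for it. An outcome definition that ignores death could therefore carry forward.

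**Working it through.** **The plan's own figure.** The documents give no admission rate, effect size or power for hospitalization. The one precision figure in Section 13, ±0.18 for the proportion retained with 20 patients, reproduces if that proportion is about 0.80 (inferred, not stated): 1.96 × √(0.80 × 0.20 / 20) = 0.175. It does not bear on hospitalization.

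**Step 1: expected deaths.** The inputs are 35-40% annualized and 20% per year (Section 2), and 20 patients (Sections 3 and 13; Section 7 says 25). With annual figure *a*, the six-month risk is 1 − exp(−a/2) if *a* is a rate, or 1 − √(1 − a) if *a* is a one-year risk.

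| *a* | Risk, as rate | Risk, as one-year risk | Deaths in 20 | P(at least one death) |
|---|---|---|---|---|
| 0.35 | 16.1% | 19.4% | 3.2-3.9 | 0.97-0.99 |
| 0.40 | 18.1% | 22.5% | 3.6-4.5 | 0.98-0.99 |
| 0.20 | 9.5% | 10.6% | 1.9-2.1 | 0.86-0.89 |

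Equal allocation would put about 10 patients at each level of a factor. With the same true risk in both groups (16% to 22.5%), a chance imbalance of two or more deaths between 10 and 10 has probability 0.35 to 0.42.

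**Step 2: hospital days.** Assume a constant death rate *r* per year and the same hospital-day rate while alive in both arms. Mean days alive out of 182 are [1 − exp(−r × 182/365)] / (r/365).

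- r = 0.35 gives 167.0 days and r = 0.70 gives 153.6 days. The ratio is 153.6/167.0 = 0.92, so the higher-mortality arm shows 8% fewer hospital days.
- Doubling from 0.20 to 0.40 gives 165.0/173.2 = 0.953, or 5% fewer. Doubling from 0.40 to 0.80 gives 150.1/165.0 = 0.910, or 9% fewer.
- Doubling the six-month risk is a larger change than doubling the rate. For 16% v 32%, 20% v 40% and 22.5% v 45%, the ratios of mean time alive are 0.904, 0.874 and 0.853, or about 10-15% fewer days.

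The ratio does not depend on the hospital-day rate, but the absolute difference does. Assuming 0.04 hospital days per day alive, with r = 0.35 v 0.70:

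- Hospital days: 0.04 × 167.0 = 6.7 v 0.04 × 153.6 = 6.1, an apparent gain.
- Days alive and out of hospital: 0.96 × 167.0 = 160 v 0.96 × 153.6 = 147.5, a loss of about 13 days.

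At 0.02 per day the hospital days are 3.3 v 3.1, and at 0.08 they are 13.4 v 12.3.

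**Step 3: counts.** With an equal admission rate while alive, the expected number of admissions falls in the same ratio as mean time alive unless time at risk is in the model. A logistic model of any admission is affected too. At an assumed 1.5 admissions per year, independent of death, the proportion ever admitted is 0.479 with 20% six-month mortality and 0.426 with 40%. At 1.0 per year it is 0.356 v 0.315, and at 2.0 per year 0.577 v 0.516.

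**Step 4: time to first hospitalization, taking deaths as censored.** If death and admission are independent, one minus Kaplan-Meier at six months is 1 − exp(−h/2) whatever the mortality; at h = 1.5 per year it is 0.528 in both arms. The comparison is unaffected and says nothing about the excess deaths.

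With dependence, it can reverse. Assume 30% of patients have 4 admissions per year and 70% have 1 per year. Their death rate is 0.15 per year in the low group and 1, 3 or 6 per year in the high group. By simulation:

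| Six-month mortality | 1 − KM, first admission | First admission or death |
|---|---|---|
| 17% | 0.520 | 0.583 |
| 28% | 0.489 | 0.597 |
| 34% | 0.461 | 0.604 |

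Time to first admission appears to improve while the composite worsens. These rates are assumptions chosen to show the mechanism.

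**The case against.** **The listed outcome need not reverse.** A reader might infer that an arm with more deaths will look better on time to first hospitalization. The documents do not support that. With independent death and admission the comparison is unchanged, and reversal needs patients prone to death to be prone to admission as well, which is plausible but assumed. This objection stands.

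**The plan states no rule that rewards death.** A reader might also infer that a patient who dies at home is, under the plan, censored with zero hospital days. Section 13 says neither. What it contains is methods with no stated place for death. This stands as to wording, but silence does not remove the problem: raw days and counts still fall when time alive is lost.

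**Mortality may be lower here.** The 35-40% describes new hemodialysis patients in general. Section 4 excludes life expectancy under six months, RRF below 2 mL/min/1.73 m², current inpatients, intended dialysis withdrawal and patients too infirm to take part in decisions. Section 2 calls RRF one of the strongest predictors of survival. The inclusion criteria set no limit on time since starting dialysis, so the prevalent rate may suit some patients. Three to five deaths is therefore an upper range; about two is still likely to matter at 10 per factor level.

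**The shift is small against the noise.** If the SD of hospital days is assumed to be 5 to 15, the 95% half-width for 10 v 10 is 2.101 × SD × √(2/10), or 4.7 to 14.1 days, against a shift of about 0.5 days (6.68 − 6.15 before rounding). This stands and limits the practical weight.

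**Deaths would be visible.** They are recorded throughout the schedule, outcomes are summarized by arm, and an independent monitor reviews all data (Section 14). That makes a misreading easier to catch, but does not correct the estimates taken into the next trial.

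**Conclusion.** The point holds for hospital days and for the number of hospitalizations. As written, death lowers both, so a higher-mortality arm can look modestly better: about 8% fewer days if the death rate doubles from 0.35 to 0.70 per year, and 5% to 9% across the protocol's own mortality figures. This rests on a constant death rate and an equal hospital-day rate while alive. The direction and percentage do not depend on the assumed day rate, but the difference in days does.

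Time to first hospitalization is blind to excess deaths rather than reversed by them, unless death and admission are positively related.

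The affected outcomes are secondary or exploratory in a pilot of about 20 patients, and the distortion is well inside sampling error. The reason to act is that the definitions and estimates are meant to inform the full-scale trial and the correction is cheap.

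**What to change.** In Sections 3 and 13:

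1. Report time to first hospitalization or death from any cause alongside time to first hospitalization. Show each component and all deaths by arm.
2. Replace raw hospital days as the analysed outcome with days alive and out of hospital from randomization to month 6. Count each day after death as 0. Where follow-up ends for another reason, such as withdrawal or transfer (Section 15), treat the remaining days as missing or censored, not as hospital-free.
3. Add a log time-at-risk offset to the Poisson model for the number of hospitalizations. A logistic model of any admission has no such term, so if that option is kept, say how deaths are counted.
4. Give raw hospital days for all randomized patients next to time alive. Do not restrict this to survivors, which would condition on an event after randomization.

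Cumulative incidence with death as a competing event, with deaths reported separately, is a legitimate alternative display for item 1.

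**Cost.** Table 1 already collects deaths and hospitalizations, so the change is mainly to protocol and analysis wording. There are two downsides. The composite mixes two kinds of event, which the component table handles. Month-6 days may also be incomplete for patients who leave the DCI clinics, since Section 15 keeps the information collected before withdrawal but sets no follow-up afterwards.

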## 5. Number of Subjects

Up to 50 patients may be recruited/consented for this study.

It is unknown, at this time, how many eligible subjects will need to be approached in order to attain the desired number of study participants. We will continue to recruit until 20 patients have been followed to completion post protocol modification.

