## 7. Study Endpoints

# DIDIT: Diuretic/Cool Dialysate Trial

- Recruit and randomize 25 incident chronic in-center HD patients with urine output >200 mL/day and to 3 mg of oral bumetanide once daily and/or to cool dialysate (35.5 °C).
- Estimate recruitment and retention rates anticipated in a full-scale study.
- Compare changes in RRF markers between groups.
- Collect preliminary data on adverse events (AE) and serious adverse events (SAE), biomarkers of inflammation and injury to native kidneys, HRQOL, health care utilization and other potential outcomes of a full-scale trial.

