## 9. Resources Available

[name], MD is the UNM Nephrologist overseeing this study. This site has been granted approval to recruit and complete study visits at the Albuquerque, New Mexico Dialysis Clinics Inc. and the Rio Rancho clinic. The PI, sub-investigators, biostatistician, micro-RNA specialist, lab staff and study coordinators and research assistants make up the study team. This team has broad expertise to successfully complete the proposed aim and efficiently deliver findings for immediate clinical and public health application.

Study physicians will be responsible for medical decision-making, and for ordering and the evaluation of necessary diagnostics and therapeutics for this study.

The 20 recruited/consented subjects that will complete this study will be recruited at the four DCI clinics in Albuquerque and at the Rio Rancho DCI clinic. The four DCI study sites should be able to supply the research subjects needed to be recruited for this study.

Recruitment will last 18 months. An additional 6 month period will be used to complete the intervention in the last subjects.

The study investigators recognize that recruitment is the major factor for a successful RCT and will use a multi-faceted approach to enhance recruitment. First, the

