## 11. Multi-Site Research

This is not a multi-site study

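### The Cox model for time to first hospitalization is committed to site and covariate adjustment that about 20–25 patients cannot carry; a two-factor model reported descriptively would serve better

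*Combined protocol and SAP*

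**What the plan says.** Section 3 (Study Design) lists "Time to first-hospitalization" as a secondary patient outcome. Section 13 (Data Analysis) examines it with Kaplan-Meier plots and then states: "To adjust for study site and baseline covariates, the proportional hazards model will be used". It names no covariates for this model; age, gender and ethnicity appear earlier in the section, as examples for the mixed model of change in residual renal function. It does not say how site or the two randomized factors enter. It gives no expected number of events, and no test or interval type for a hazard ratio. All analyses are intention-to-treat.

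The size of the trial is stated in several ways:
- Section 3: "randomizing 20 chronic hemodialysis patients from DCI centers".
- Section 7: "Recruit and randomize 25 incident chronic in-center HD patients".
- Section 5: "We will continue to recruit until 20 patients have been followed to completion post protocol modification", with up to 50 consented, so the analysed set may exceed 20.

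The number of sites also varies. Section 9 has patients "recruited at the four DCI clinics in Albuquerque and at the Rio Rancho DCI clinic", which is five clinics, and then says "The four DCI study sites should be able to supply the research subjects". Section 11 says "This is not a multi-site study". Section 4 describes randomization to the four arms and mentions no stratification by site.

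**The concern.** A Cox model draws its information from events, not patients. With 20–25 patients there will be few first hospitalizations, and the stated rule spends several coefficients on site and an open number on covariates. The treatment estimate can then become infinite, or its interval can miss the true value more often than its label says. Because the covariates and site coding are left open, they could also be chosen after the data are seen. This model is the only effect estimate planned for a named secondary outcome.

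**Working it through.** **The plan's own figure.** There is none for this outcome. The only precision figure in Section 13 is ±0.18 for the proportion retained among 20. It reproduces as 1.96 × √(0.8 × 0.2 / 20) = 0.175 if retention is about 0.8, which the plan does not state. It says nothing about the Cox model.

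**Coefficients.** Two randomized factors, plus 3 terms for four clinics or 4 terms for five, give 2 + 3 = 5 or 2 + 4 = 6. Carrying over age, gender and ethnicity (an assumption) adds 3, giving 8 or 9.

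**Events.** The share hospitalized by 6 months is assumed to be 20–70%.
- n = 20: 0.2 × 20 = 4 to 0.7 × 20 = 14 events.
- Six coefficients: 4/6 = 0.7 to 14/6 = 2.3 events each.
- Nine coefficients: 4/9 = 0.4 to 14/9 = 1.6 each.
- If all 20 patients were hospitalized, six coefficients would have 20/6 = 3.3 each.

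**Null simulation, n = 20.** Exponential times were censored at 6 months, with balanced factorial cells, patients spread at random over clinics, and 1,000 runs per setting. The Monte Carlo standard error is about 0.7 points at 5% and 1.1 at 15%. Entries are percentages of trials at 20/35/50/70% hospitalized (about 4/7/10/14 events). Wald error counts an infinite estimate as no rejection.

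| Model | Coefficients | Treatment hazard ratio infinite | Likelihood-ratio error | Wald error |
|---|---|---|---|---|
| Two factors only | 2 | 20/3/0.2/0 | 7/9/5/5 | 0/2/4/5 |
| Plus four clinics | 5 | 33/7/1/0.2 | 13/12/12/12 | 1/4/8/9 |
| Plus five clinics | 6 | 34/9/0.5/0.1 | 15/13/12/12 | 1/4/8/10 |
| Plus five clinics and three covariates | 9 | 72/30/6/1 | 26/28/22/18 | 1/5/12/15 |
| One site term plus age | 4 | 23/5/0.5/0 | 14/11/10/8 | 1/4/6/7 |
| Stratified by five clinics, plus age | 3 | 43/12/4/1 | 15/12/9/8 | 0/0.5/2/4 |

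Under the null, profile-likelihood coverage is 100 minus the likelihood-ratio error, so 85/87/88/88% with five clinics. Wald 95% limits for that model, when finite, cover 99/95/92/90%. Repeats with separately written code gave likelihood-ratio errors of 16/11/11/11% and 13/14/11/13% for six coefficients, 25/28/21/17% and 21/26/22/17% for nine, and 8/8/6/6% and 9/7/7/6% for two.

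**Larger n.** At n = 25, six coefficients give infinite estimates in 18/2/0.4/0% and likelihood-ratio error of 12/10/11/10%. Nine give 44/9/1/0.1% and 23/19/16/13%. At n = 50, the ceiling on consents, nine coefficients give Wald error of 7–9% among fits that converged, with fit failure in 21/3/0.5% at 30/50/70% hospitalized.

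**The two-factor alternative.**
- With Firth's penalty, its likelihood-ratio error at n = 20 is 3/6/6/4%.
- With prognostic age (log hazard ratio 0.5 per SD) and site effects (SD 0.5) left out of the model, it is 3/6/4/8%. The five-clinic model under the same effects gives 14/13/12/12%.
- Stratified by site without covariates, Firth error is 4/4/6/6%, with no usable information in 4% of runs at the lowest rate.

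**Precision.** The median ratio of upper to lower 95% limit at n = 20 is 51/25/13/9-fold for two factors (unpenalized), against 122/45/23/15-fold with five clinics. The large-sample formula exp(2 × 1.96 × 2/√d) gives 50-fold at d = 4 events and 8-fold at d = 14, which agrees with the two-factor figures. For an assumed hazard ratio of 0.5, 80% power needs 4 × (1.96 + 0.84)² / (ln 0.5)² ≈ 66 events.

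**The case against.** The plan fixes no test or interval type for the hazard ratio; Section 13 attaches its 95% intervals to mean changes. The largest errors above belong to likelihood-ratio tests and profile limits. An analyst who used Wald limits, with one site term or with stratification by site, would be close to nominal or conservative. This stands, and it limits the claim.

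A reader might infer that the adjusted model will usually fail to give an estimate. The documents do not support that. With site terms alone the treatment estimate is infinite in 1% of trials or fewer at 50–70% hospitalized. The 72% figure needs about 4 events and three covariates that the plan never assigns to this model. A cruder count, which includes failure of any coefficient or of the fit, reaches 88/56/25% at 30/50/70% hospitalized with nine coefficients, but much of that is not failure of the treatment term.

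It can also be said that naming a few covariates and the site coding would close the gap. That would remove the post-hoc choice. It would not repair the likelihood-ratio error, which is already about 12–15% with site terms and no covariates. Nor is the two-factor model perfect: with strong omitted prognostic effects its error reached 8% at 70% hospitalized.

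Finally, the analysed set may exceed 25, and the problem shrinks as it grows. This is true, though at 50 the nine-coefficient model still runs at 7–9%.

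**Conclusion.** The concern holds, with minor impact. Following Section 13 as written gives 5–6 coefficients before any covariate, on about 4–14 events at n = 20. Likelihood-ratio error is then about 12–15% (11–16% across repeats), and about 17–28% with nine coefficients. Wald limits with site terms are conservative at low event rates and cover about 90–92% at 50–70% hospitalized; with nine coefficients Wald error there is about 10–15%. Infinite estimates are a concern mainly at about 7 events or fewer.

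These sizes rest on an assumed hospitalization rate, null effects, equal clinic sizes and, for nine coefficients, an assumed covariate list. Section 1 refers to frequent hospitalizations and Section 6 gives 8 months' participation, so the higher rates may be the more relevant ones.

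A reader might go on to infer that the pilot's conclusions or the design of the larger trial are compromised. The documents do not support this. The outcome is secondary, Kaplan-Meier plots are also planned, and Section 13 names retention, mean changes and variability, not a hazard ratio, as what the pilot will supply.

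**What to change.** In Section 13, replace the adjustment sentence with wording to this effect:

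- The main Cox model for time to first hospitalization contains only the two randomized factors (bumetanide vs placebo; 35.5 vs 37 °C dialysate).
- It is reported descriptively, with event counts and 95% confidence intervals of a stated type, beside Kaplan-Meier curves by each factor.
- Firth's penalized likelihood with profile limits is used if there are fewer than about 8 events in total, with the threshold fixed in advance.
- Site adjustment is a sensitivity analysis only: the same two-factor model stratified by site, without covariates. This also covers the case where randomization is stratified by site, which the documents do not state. If randomization is balanced within site, simulated Firth error is 3/3/5/5% unstratified and 4/4/5/6% stratified.

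Most of the gain comes from dropping terms; the penalty mainly removes infinite estimates when events are few.

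The cost is SAP wording. The penalty, profile limits and stratification are standard options in SAS, the planned software. The price is that there is no covariate-adjusted hazard ratio as the main result, and the estimate stays very imprecise (limits still 9- to 51-fold apart at n = 20), which is the reason to call it descriptive.

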## 6. Study Timelines

- The duration of an individual subject's participation in this research is 8 months.
- Subject recruitment will occur over 18 months.
- See table 1 "*Schedule of study tests/assessments/intervention*", Study Procedures section 12, for procedure timeline.
- Anticipated data collection is to be completed by the end of year 2. Once all data has been collected and verified, data analysis and report preparation will take place over a 6 month period.

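### The target size is not reconciled (20 randomised, 25 randomised, or recruit until 20 complete), and the only precision statement belongs to just one of the three

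*Combined protocol and SAP*

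**What the plan says.** The current text of the combined protocol and SAP gives the target in five places.

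- **Section 3 (Study Design):** the trial proceeds "by randomizing 20 chronic hemodialysis patients from DCI centers in the greater Albuquerque area".
- **Section 13 (Data Analysis):** "With a recruitment and randomization of 20 patients, the proportion retained can be estimated to within" ±0.18, with a 95% confidence interval. No retention proportion is given, and there is no power calculation.
- **Section 7 (Study Endpoints):** "Recruit and randomize 25 incident chronic in-center HD patients with urine output >200 mL/day".
- **Section 5 (Number of Subjects):** "We will continue to recruit until 20 patients have been followed to completion post protocol modification". The same section caps consent at 50 people, and Sections 3, 6 and 9 limit recruitment to 18 months.
- **Section 9 (Resources Available):** "The 20 recruited/consented subjects that will complete this study", so the same 20 are described both as consented and as completing.

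Section 7 also lists this as an endpoint: "Estimate recruitment and retention rates anticipated in a full-scale study". No section gives a dropout allowance or defines when a patient counts as retained.

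**The concern.** Sections 3 and 13 count patients randomised and say 20. Section 7 also counts patients randomised and says 25. Section 5 counts completers and leaves the number randomised to be settled by dropout, within the consent cap and the recruitment window. These are different enrolment rules, and no sentence connects them. Section 5 ties its count to a protocol modification, but nothing says whether the 25 in Section 7, or the 20 elsewhere, includes patients randomised earlier.

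Estimating retention is a declared endpoint of this pilot, and the ±0.18 sentence is the only reason offered for its size. As written, staff cannot tell which count ends randomisation, and a reader cannot tell which design the stated precision describes. The Section 5 rule also differs in kind from the others. It fixes the number of completers (the numerator of the retention proportion) and leaves the denominator random, so a statement for a fixed 20 randomised does not describe it.

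**Working it through.** **Inputs.** From the documents: 20 randomised (Sections 3 and 13), 25 randomised (Section 7), 20 completers (Section 5), a 95% interval and ±0.18 (Section 13). The retention proportion p is not in the documents. Every value of p below is an assumption.

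**Step 1. Reproduce ±0.18.** The normal-approximation half-width is 1.96 × √(p(1−p)/n). With n = 20 and p = 0.80, it is 1.96 × √(0.16/20) = 0.175, which rounds to 0.18. Any p from about 0.77 to 0.80 rounds to the same figure.

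**Step 2. Find when ±0.18 holds.** Set the half-width to 0.18 with n = 20. Then p(1−p) = 0.18² × 20 / 1.96² = 0.1687, so p = 0.785. For retention between 50% and 78.5% the interval is wider than stated. The largest value, at p = 0.50, is 1.96 × √(0.25/20) = 0.219.

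**Step 3. Compare the three rules.** If recruitment runs until 20 complete, the approximate (delta-method) half-width is 1.96 × p × √((1−p)/20).

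| Assumed retention | 20 randomised | 25 randomised | Until 20 complete |
|---|---|---|---|
| 70% | 0.201 | 0.180 | 0.168 |
| 80% | 0.175 | 0.157 | 0.157 |
| 90% | 0.131 | 0.118 | 0.125 |

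Relative to 20 randomised, the half-width is multiplied by √(20/25) = 0.894 for 25 randomised, and by √p for the completer rule. Both factors are below 1 (for p below 1), so 20 randomised gives the widest interval of the three. The maxima are 0.219 for 20 randomised and 0.196 for 25 randomised (both at p = 0.50). For the completer rule the maximum is 0.169, at p = 2/3.

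**Step 4. Link patients randomised to completers.**

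| Assumed retention | Expected completers of 20 | Chance all 20 complete (p²⁰) | Expected number randomised for 20 completers (20/p) | 5th–95th percentile | Chance at least 20 of 25 complete |
|---|---|---|---|---|---|
| 70% | 14 | 0.001 | 28.6 | 23–35 | 0.19 |
| 80% | 16 | 0.012 | 25.0 | 21–29 | 0.62 |
| 90% | 18 | 0.12 | 22.2 | 20–25 | 0.97 |

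The percentiles come from the negative binomial distribution of the number randomised when the 20th completer is reached. The last column is a binomial tail. Section 5 and Section 7 agree in expectation only at p = 20/25 = 0.80. Section 3 and Section 5 agree only with no dropout.

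**The case against.** Several points on the other side have weight.

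- **The figures might coexist.** A reader might infer that 20 and 25 randomised contradict each other whatever the retention. That is too strong. The 25 could be a whole-study total and the 20 a count after the modification, and 25 randomised with 20 completing fits 80% retention exactly. But no section says either thing, so the fair description is unreconciled.
- **Enrolment is bounded.** A reader might infer that Section 5 leaves enrolment without limit. It does not: at most 50 may be consented, within 18 months. The cap counts people consented, however, and under Section 4 the 24-hour urine result that decides eligibility comes after consent. So the cap is not a target for the number randomised.
- **The stated precision errs on the safe side.** A reader might infer that ±0.18 is wrong or flatters the design. Steps 1 and 3 show otherwise. This objection stands: the harm is unclear text, not overstated precision. It holds as long as recruitment reaches the chosen target.
- **The end of follow-up is probably consistent.** Section 3 says of the last subjects that "they will be re-assessed at month 8 for an end of study evaluation", Section 6 says that "participation in this research is 8 months", and Table 1 stops at column 7. A reader might infer a conflict. But Table 1's own title gives 4 + 24 + 4 = 32 weeks, which is eight 4-week periods in columns 0 to 7, so month 8 can be the last column. What remains is minor: no time point is attached to being retained or to being followed to completion.

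**Conclusion.** The point holds as an unreconciled sample-size target. Three enrolment rules stand in the current text, nothing connects them, and the single precision statement describes only one. The ±0.18 is arithmetically sound at about 77% to 80% retention. It lacks the assumption it depends on, and it is not a maximum (0.22 at n = 20).

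The size in precision terms is modest: 0.175 against about 0.157 at 80% retention, with the plan's figure on the conservative side. The size in enrolment terms is larger. At 80% retention, 20 randomised yields about 16 completers, whereas 20 completers needs about 25 randomised (5th–95th percentile 21–29). The existence of the conflict rests on the text alone. Its numerical size rests on assumed retention, since the documents give none. It should be fixed, and text edits are enough.

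**What to change.** Choose one rule and use it in Sections 3, 5, 7, 9 and 13. State the retention assumption, and say whether patients randomised before the modification count. Any of these would do (95% interval, normal approximation):

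- **(a) Fix about 25 randomised**, expected to give 20 completers at an assumed 80% retention. Replace the recruit-until sentence in Section 5. Precision: ±0.16 at 80% retention, at most ±0.20.
- **(b) Fix 20 randomised.** Remove the recruit-until sentence from Section 5, reword Section 9 and change 25 to 20 in Section 7. Precision: ±0.18 at 80% retention, at most ±0.22.
- **(c) Keep 20 completers as in Section 5**, the only rule tied to the protocol modification. State the expected number randomised (about 25 at an assumed 80%; 5th–95th percentile 21–29) and a maximum number randomised within the cap of 50 consented and the 18-month window. Align Sections 3, 7, 9 and 13. Precision: about ±0.16 at 80% retention, with a note that the number randomised is not fixed.

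In every option, calculate retention over all randomised patients, and use one completion time point for both being retained and being followed to completion.

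**Cost.** A protocol amendment with text edits, and no new procedures. Options (a) and (b) do not guarantee 20 completers: with 25 randomised the chance of at least 20 is 0.62 at 80% retention, and with 20 randomised about 16 are expected. Option (a) also randomises five more than Sections 3 and 13 state. Option (c) leaves the number randomised open up to its maximum. The worst-case precision, once stated for (a) or (b), is slightly less favourable than ±0.18.
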